#### **6.2.8. Graphical Displays**

For SALT and ALODEX, the LS mean percent change and 95% CI will be plotted over time by treatment group. For the binary efficacy endpoint of proportion of subjects achieving  $\geq 50\%$  hair regrowth relative to baseline based on the SALT and ALODEX scores, the percentage and 95% CI will be plotted over time by treatment group.

### **6.3. SAFETY**

All safety analyses will be performed on the Safety Population. Values for all safety variables will be listed by subject and visit (as applicable).

### **6.3.1. Adverse Events**

Adverse events will be mapped to a preferred term and system organ classification by Medical Dictionary for Regulatory Activities (MedDRA) version 22.0.

An overall summary will be presented which includes the number of TEAEs and the number and percentage of subjects who experienced at least one TEAE. This summary will also include:

- Any TEAE
- Any Serious TEAE
- Any Mild TEAEs
- Any Moderate TEAEs
- Any Severe TEAEs
- Any Related TEAEs
- Any TEAEs leading to discontinuation
- Any Related TEAEs leading to discontinuation

Additional summaries of TEAEs will be provided showing the number and percentage of subjects who experienced at least one TEAE. These summaries will be presented by system organ class (SOC), preferred term (PT) and maximum severity. If a participant reports the same PT multiple times within the same SOC, that PT will only be counted once within that SOC for that participant. As with the PT, if a participant reports multiple conditions within the same SOC, that SOC will only be counted once for that participant. In the summary, SOC will be listed in ascending alphabetical order; PTs will be listed in order of descending frequency for all participants within each SOC.

The occurrence of TEAEs related to study medication will be tabulated by SOC, PT and maximum severity. Serious adverse events (SAE) will be presented by system organ class (SOC), preferred term (PT) and maximum severity. SAE related to study medication will also be presented by SOC and PT.

All AEs reported will be listed by individual subject, showing both verbatim and preferred terms. All AEs reported with a start date prior to the initiation of study medication will be excluded from the TEAE tables but will be included in the listings.

Missing onset dates will be imputed as previously outlined in Section 3.3.5 as required to determine TEAEs.

### **6.3.2. Clinical Laboratory Assessments, Vital Signs, and Physical Examination Findings**

Descriptive summaries of quantitative clinical laboratory results (hematology, chemistry, and urinalysis) and their change from baseline values will be presented by study visit and treatment group. Observed values of categorical urinalysis data will be displayed with frequencies and percentages. All laboratory data will be listed for individual subjects.

Treatment-emergent abnormal laboratory assessments will be based on the lab-provided normal ranges. If the baseline laboratory assessment is normal and shifts to Low or High post-baseline,

then the laboratory value is considered a TE abnormal laboratory value. For each protocol specified lab test, the number and percent of subjects reporting a TE abnormal lab will be reported.

All laboratory summaries will be limited to the tests specified in the protocol.

Descriptive summaries of vital signs and their change from baseline will be presented by study visit and treatment group and all vital signs will be listed.

Post-baseline PE findings will be listed.

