**Table 2: Study Medication Interruption Criteria**

Laboratory Test	Hold Study Medication if:	Resume Study Medication if:
WBC count	< 2 x 10  /μL	≥ 2.5 x 10  /μL
ANC	< 1 x 10  /μL	≥ 1.5 x 10  /μL
Lymphocyte count	< 0.5 x 10  /μL	≥ 0.75 x 10  /μL
Platelet count	< 75 x 10  /μL	Returns to Baseline values
Hemoglobin	< 8 g/dL or a decrease > 2g/dL	≥ 10 g/dL
AST or ALT	> 3 x ULN	< 2 x ULN or within 20% of Baseline values
Serum creatinine	>2 x ULN	<1.5 x ULN or within 10% of Baseline value

Subjects with one or more of the Screening (Visit 1) laboratory values meeting the Study Medication Interruption Criteria found in [Table 2](#) must have repeat lab testing performed with results meeting the minimum criteria for resumption in order to initiate treatment at Baseline (Visit 2).

During treatment, if a subject has one or more of the abnormal laboratory values noted in [Table 2](#), the investigator or designee upon receipt and review of the central laboratory report should instruct the subject to hold study medication dosing. The investigator or designee should ask the subject about symptoms, concomitant illnesses and medications and repeat the test(s) as soon as possible. The Medical Monitor must be notified of dose interruptions due to SAEs considered related to study medication or laboratory abnormalities noted in [Table 2](#).

If the retest confirms the abnormal laboratory value, then the study medication should continue to be held followed by repeat testing once a week or sooner at the discretion of the investigator. The subject should be followed until the laboratory abnormality(s) returns to normal or to Baseline values.

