### Treatment-emergent Laboratory Abnormalities

A treatment-emergent laboratory abnormality is defined as a result in which the baseline value is within normal laboratory limits and the post-baseline value is outside normal laboratory limits. If the relevant baseline assessment is missing, then any post-baseline value outside normal laboratory limits is treatment-emergent.

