## **6. STATISTICAL METHODS**

Descriptive statistical methods will also be used to summarize the data from this study, with hypothesis testing performed for the primary and key secondary efficacy endpoints. Unless stated otherwise, the term “descriptive statistics” refers to number of subjects, mean, median, standard deviation, minimum, and maximum for continuous data, and frequencies and percentages for categorical data. For categorical variables, the denominator of percentages will be the number of subjects in the treatment group, except for those collected by study visit and/or scheduled time point, in which case the denominator of percentages will be the number of subjects with a non-missing value at the visit and/or the scheduled time point. If a different denominator is used, this will be identified in the summary table.

All data collected during the study will be included in data listings. Unless otherwise noted, the data will be sorted first by treatment group, subject number, and then by date within each subject number.

The term ‘treatment group’ refers to ATI-501 active groups and matching Placebo Oral Suspension group.

All statistical testing will be two-sided and will be performed using a significance (alpha) level of 0.05 unless otherwise stated. P-values will be presented to three decimal places. For the efficacy

endpoints, the ATI-501 treatment groups will be tested versus Placebo Oral Suspension via statistical inference.

The statistical analyses will be conducted with the SAS® software package version 9.4 or higher. All analyses will be subject to formal verification procedures. Specifically, results will be independently verified by a second programmer/statistician prior to issuance of the draft statistical report. All documents will be reviewed by the lead statistician to ensure accuracy and consistency.

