## 8. PROGRAMMING CONVENTIONS

- Page orientation, margins, and fonts: Summary tables, listings, and figures will appear in landscape orientation. There should be a minimum of a 1” boundary on the upper (bound) edge, and a minimum of a 1.0” boundary on the remaining three edges. Output should be printed in Courier New with a point size of 8. Titles may be printed using a larger font (e.g., Arial point size 10).
  - Identification of analysis population: Every summary table and figure should clearly specify the analysis population being summarized. Listings will be prepared for all subjects.
  - Group headers: In the summary tables, the group headers will identify the summary group and the sample size for the indicated analysis population. Of note, the header’s sample size does not necessarily equal the number of subjects summarized within any given summary module; some subjects in the analysis population may have missing values and thus may not be summarized.
  - Suppression of percentages corresponding to null categories: When count data are presented as category frequencies and corresponding percentages, the percent should be suppressed when the count is zero in order to draw attention to the non-zero counts.
  - Presentation of sample sizes: Summary modules should indicate, in one way or another, the number of subjects contributing to the summary statistics presented in any given summary module. As mentioned above, this may be less than the number of subjects in the analysis population due to missing data.
    - In the quantitative modules describing continuous variables (and thus presenting sample size, means, and standard deviations), the sample size should be the number of non-missing observations. The number of missing observations, if any, will be noted.
    - For categorical variables that are presented in frequency tables, the module should present the total count in addition to the count in each category. Percentages should be calculated using this total as the denominator, and the percentage corresponding to the sum itself (that is, 100%) should be presented to indicate clearly to a reviewer the method of calculation. The number of missing observations, if any, will be noted.
  - Sorting: Listings will be sorted by treatment group, subject number and date, if applicable.

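### The treatment-emergent laboratory tables count new low and new high values as one event per test, which weakens the contrast between arms when a drug effect runs one way

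*SAP*

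**What the plan says.** SAP 4.3.6 defines a treatment-emergent laboratory abnormality as a result where "the baseline value is within normal laboratory limits and the post-baseline value is outside normal laboratory limits". No direction is given. It adds a rule for gaps: "If the relevant baseline assessment is missing, then any post-baseline value outside normal laboratory limits is treatment-emergent".

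SAP 6.3.2 repeats the definition for the analysis. The flag is raised "If the baseline laboratory assessment is normal and shifts to Low or High post-baseline", and for each protocol-specified test "the number and percent of subjects reporting a TE abnormal lab will be reported". This section does not mention missing baselines or a denominator. The titles of Tables 14.3.4.1.2 (hematology), 14.3.4.2.2 (chemistry) and 14.3.4.3.2 (urinalysis) show no split by direction.

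Three statements bear on the denominator. SAP 6 gives a default for categorical variables: "the denominator of percentages will be the number of subjects in the treatment group". For variables collected by visit it makes an exception: "the denominator of percentages will be the number of subjects with a non-missing value at the visit". It also says that any other denominator will be identified in the table. SAP 8 has frequency tables show a total count and says "Percentages should be calculated using this total as the denominator".

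In the protocol, the "Hold Study Medication if" column of Table 2 lists low WBC, neutrophils, lymphocytes, platelets and hemoglobin, and high AST/ALT and serum creatinine. The permanent discontinuation criteria in Protocol 3.4.1.2 keep the same directions for these tests.

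**The concern.** A subject whose neutrophils newly fall below range and one whose neutrophils newly rise above it add to the same cell. The protocol's own laboratory safety rules treat only one of those directions as a reason to act. Opposite-direction events in the background raise the printed percentage in every arm and so reduce the ratio between arms. If the drug also shifts the whole distribution, it removes some opposite-direction events from the active arms, and the difference between arms shrinks too.

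Safety is part of the primary objective, and each arm has about 95/4 = 23.75, or 24, subjects. At that size the planned counts should be as easy to interpret as possible. A secondary question is whether subjects who can never be counted sit in the denominator.

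**Working it through.** The documents state no figure for these tables and no laboratory event rates, so there is nothing to reproduce. The sizes below are illustrations on stated assumptions.

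**1. Direction.** SAP 4.3.6 (outside limits), SAP 6.3.2 (Low or High) and the table titles all give one flag and one count per test. Protocol Table 2 and 3.4.1.2 give one direction per test. The merging is in the text and is not an inference.

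**2. Size under a distribution shift.** Assumptions: normally distributed analyte; limits at ±1.96 SD; baseline in range; seven post-baseline visits (Visits 3 to 9); within-subject correlation 0.7; the drug lowers every subject's mean by the same amount. Simulated share of subjects ever flagged, for a 0.5 SD fall:

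- Low only: 7.3% on placebo, 20.0% on drug. Ratio 20.0/7.3 = 2.7; difference 12.7 points.
- Low or High: 14.8% on placebo, 21.9% on drug. Ratio 21.9/14.8 = 1.5; difference 7.1 points.
- Share of the difference lost: (12.7 − 7.1)/12.7 = 44%.

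The loss equals the fall in subjects flagged High only: (14.8 − 7.3) − (21.9 − 20.0) = 7.5 − 1.9 = 5.6 points. In this model it can never exceed the placebo High-only rate of 7.5 points, so its share shrinks as the drug effect grows:

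| Assumed drug effect (correlation 0.7) | Risk ratio, Low only | Risk ratio, pooled | Share of difference lost |
|---|---|---|---|
| 0.5 SD fall, all subjects | 2.7 | 1.5 | about 44% |
| 1.0 SD fall, all subjects | 5.4 | 2.7 | 22% |
| 1.5 SD fall, all subjects | not tabulated | not tabulated | 13% |
| 2 SD fall in a quarter of subjects | not tabulated | not tabulated | 10% |

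At 0.5 SD, varying the correlation from 0.6 to 0.8 moves the share lost only within about 40% to 46%.

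**3. Size under a fixed background.** Assume Low and High are independent, so pooled = 1 − (1 − Low)(1 − High). Take Low as 5% on placebo and 25% on active: ratio 5.0, difference 20 points.

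| High, placebo / active | Pooled, placebo / active | Ratio | Difference |
|---|---|---|---|
| 0% / 0% | 5% / 25% | 5.0 | 20 points |
| 5% / 5% | 9.8% / 28.8% | 2.95 | 19 points |
| 10% / 10% | 14.5% / 32.5% | 2.24 | 18 points |
| 20% / 20% | 24% / 40% | 1.67 | 16 points |
| 10% / 2% | 14.5% / 26.5% | 1.83 | 12 points |

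With an equal background the ratio suffers far more than the difference. With no opposite-direction events nothing is lost.

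**4. Denominator.** Under the SAP 6 default, its by-visit exception or the SAP 8 total, a subject with an out-of-range baseline may stay in the denominator although the definition prevents that subject from being counted. Printed percent = at-risk percent × (1 − share with an out-of-range baseline). An at-risk 25% prints as 25 × 0.95 = 23.75% if the share is 5%, as implied by a central 95% range, and as 25 × 0.80 = 20% if the share is 20%. The documents do not give the share. If it is equal across arms, the ratio is unchanged.

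**The case against.** The strongest reply is that direction is not lost from the study. SAP 6.3.2 summarizes quantitative values and change from baseline by visit and arm. SAP 6 includes the minimum and maximum in those summaries, so a downward shift or an extreme low would show. All laboratory data are listed, with a separate listing of abnormalities. Protocol 8.1.5 requires clinically significant out-of-range results after first treatment to be reported as adverse events, so they reach the adverse event tables by arm. The tables in question are descriptive, with no test attached.

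All of that stands, and it rules out a reading that a reader might be tempted to make: that a cytopenia or enzyme signal would be hidden. It does not replace the count. Means by visit can miss a few subjects crossing a limit, listings give no rate by arm, and adverse event reporting depends on the investigator's judgment of significance. Protocol 9.5 promises a tabulation of clinically significant laboratory results, but the SAP's list of tables contains none under that name.

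Two further strong readings are not supported. The first is that the table divides by everyone in the arm and so understates the percentages. SAP 6.3.2 names no denominator, laboratory tests are collected by visit, and SAP 6 and SAP 8 can be read differently. Moreover, pooling the directions raises the printed percentage; only the denominator can lower it. The second is that roughly two fifths of any effect disappears. That is the small-shift, symmetric-range case only. Nor does the denominator bias the randomized comparison in expectation. Exclusion criterion 14, on neutrophils and platelets, should also keep low baselines uncommon for those two tests.

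**Conclusion.** The point holds for direction. The TE laboratory tables merge new low and new high values, although each of the protocol's laboratory hold and stop rules runs one way. Opposite-direction background events weaken the contrast between arms for a one-directional effect.

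On the assumed model the risk ratio is roughly halved at falls of 0.5 and 1.0 SD. The share of the risk difference lost is much smaller for larger effects than for a 0.5 SD fall. The true size cannot be computed from the documents, and it is zero for a test with no opposite-direction events.

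The denominator is a lesser matter. It is not clearly stated and not limited to subjects at risk, which can lower the printed level by an unknown factor without favoring an arm in expectation.

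The change is worth making before the SAP is applied, because this is the only planned SAP count of subjects with new out-of-range values by arm and it should show which way they went.

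**What to change.** In SAP 4.3.6, SAP 6.3.2 and Tables 14.3.4.1.2, 14.3.4.2.2 and, for quantitative tests, 14.3.4.3.2:

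- Report TE-Low and TE-High as separate rows for each test.
- In each row, count any shift into that direction. A subject above range at baseline who later falls below range then counts as TE-Low; the present definition never counts that subject.
- Use as denominator the subjects with at least one post-baseline value for the test whose baseline is missing or not already abnormal in that direction, and print that n.
- State the same missing-baseline rule in 4.3.6 and 6.3.2. At present only 4.3.6 has one.

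The cost is SAP wording, table shells and longer tables. No new data are needed.

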### **6.3.3. Other Safety Analyses**

ECG measurements will include heart rate, QT interval, Fredericia-corrected QT interval (QTcF), PR interval, and QRS interval. Change from baseline will be summarized descriptively by treatment group at each scheduled evaluation and all ECG data will be listed. Proportion of subjects with abnormal ECG interpretations (CS and NCS) will be summarized at each study visit and by treatment group. Proportion of subjects who meet each of the following criteria from International Conference on Harmonization Guideline E14 “Clinical Evaluation of QT/QTc Interval Prolongation and Proarrhythmic Potential for Non-Antiarrhythmic Drugs” (October 2005) for QT and corrected QT intervals will be summarized across treatment groups:

- QT or QTcF >450 milliseconds (msec)
- QT or QTcF >480 msec
- QT or QTcF >500 msec
- QT or QTcF increases from baseline by  $\geq 30$  msec
- QT or QTcF increases from baseline by  $\geq 60$  msec

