  - New finding of QRS  $> 120\text{ms}$  (if not present at screening. For example, subjects with right bundle branch block at screening would not need to be withdrawn from the study if their subsequent ECGs remained unchanged).
  - Evidence of QT-interval prolongation, defined as an increase in the QTcF interval  $> 60\text{ms}$  from Visit 1
  - Acute signs of ischemia or infarction
  - Any ECG abnormality which may, in the opinion of the investigator, represent a new medical issue of concern

Site staff must perform protocol-required procedures for trial discontinuation and follow-up.

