  - Topical treatments on the scalp with anthralin, bimatoprost, corticosteroids, diphencyprone, diphenylcyclopropanone (DPCP), squaric acid dibutylester (SADBE), minoxidil, pimecrolimus, or tacrolimus within 1 month of Baseline (Visit 2).
  - Phototherapy (narrow band Ultraviolet B [NB UVB] or broadband therapy) within 4 weeks of Baseline (Visit 2).
16. Participation in an investigational drug or device trial in which administration of an investigational drug or device occurred within 30 days or 5 half-lives (whichever is longer) of Baseline (Visit 2).
17. Any condition possibly affecting oral drug absorption, e.g., gastrectomy, clinically significant diabetic gastroenteropathy, or certain types of bariatric surgery such as gastric bypass. Procedures such as gastric banding are not exclusionary.
18. Sensitivity to any of the ingredients in the study medications.
19. Unwillingness to refrain from weaves, hair extensions, or shaving of the scalp for at least two weeks prior to a study visit, at the discretion of the investigator, based on the ability to assess hair growth.
20. Screening ECG findings of:
  - QTcF  $>450\text{msec}$  for males or  $>470\text{msec}$  for females (use of the ECG algorithm is acceptable for this purpose)
  - Heart rate  $\leq 45$  or  $\geq 100$  beats/minutes (A subject with a heart rate  $\leq 45$  beats/min may be enrolled if in the opinion of the investigator the heart rate is not clinically significant).
  - Rhythm disturbance other than sinus arrhythmia or ectopic supraventricular rhythm (ectopic atrial rhythm)

- Conduction disturbance including PR >240msec, pre-excitation (delta wave and PR <120msec), second degree or higher AV block
  - Acute or chronic signs of ischemia
  - Left Bundle Branch Block
  - Prior myocardial infarction
21. Vaccination with a live or attenuated vaccine within 6 weeks prior to Baseline (Visit 2) or planned vaccinated with these vaccines at any time during treatment or within 6 weeks following discontinuation of study medication.
  22. Participation in an investigational study with ATI-502 Topical Solution.
  23. Subjects unwilling to have photographs taken for study purposes.

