#### Section 14.3 Safety

- 113. Table 14.3.1.1 Overall Summary of Adverse Events, Safety Population
- 114. Table 14.3.1.2 Treatment-Emergent Adverse Events by System Organ Classification, Preferred Term, and Greatest Severity, Safety Population
- 115. Table 14.3.1.3 Treatment-Emergent Adverse Events by System Organ Classification and Preferred Term, Safety Population
- 116. Table 14.3.1.4 Treatment-Emergent Serious Adverse Events by SOC and PT, Safety Population

- 117. Table 14.3.1.5 Treatment-Emergent Adverse Events Related to Study Drug by SOC and PT, Safety Population
- 118. Table 14.3.1.6 Treatment-Emergent Adverse Events Leading to Discontinuation of Study Drug by SOC and PT, Safety Population
- 119. Table 14.3.1.7 Study Drug Related Treatment-Emergent Adverse Events Leading to Discontinuation of Study Drug by SOC and PT, Safety Population
- 120. Table 14.3.4.1.1 Summary of Hematology Results and Change from Baseline by Visit, Safety Population
- 121. Table 14.3.4.1.2 Summary of Treatment-Emergent Abnormal Hematology Results, Safety Population
- 122. Table 14.3.4.2.1 Summary of Serum Chemistry Results and Change from Baseline by Visit, Safety Population
- 123. Table 14.3.4.2.2 Summary of Treatment-Emergent Abnormal Serum Chemistry Results, Safety Population
- 124. Table 14.3.4.3.1 Summary of Urinalysis Results and Change from Baseline by Visit, Safety Population
- 125. Table 14.3.4.3.2 Summary of Treatment-Emergent Abnormal Urinalysis Results, Safety Population
- 126. Table 14.3.5.1.1 Summary of ECG Results and Change from Baseline by Visit, Safety Population
- 127. Table 14.3.5.1.2 Proportion of Subjects with Abnormal ECG Interpretations, Safety Population
- 128. Table 14.3.5.1.3 Proportion of Subjects with Noteworthy QT and QTcF Values and Changes from Baseline by Visit
- 129. Table 14.3.5.2.1 Summary of Vital Signs and Change from Baseline, Safety Population

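### The absolute QT limits in SAP 6.3.3 do not require a new crossing, and the "QT or QTcF" wording, if tabulated as one row, lets a fall in heart rate alone meet any of the five criteria

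*SAP*

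**What the plan says.** SAP 6.3.3 plans two kinds of numerical ECG summary. The continuous one covers heart rate, QT, QTcF, PR and QRS: "Change from baseline will be summarized descriptively by treatment group at each scheduled evaluation and all ECG data will be listed". The categorical one gives the proportion of subjects meeting criteria that the SAP attributes to an ICH guideline, "for QT and corrected QT intervals will be summarized across treatment groups". There are five criteria. The first is "QT or QTcF >450 milliseconds (msec", and the next two repeat it at 480 and 500. The last two begin "QT or QTcF increases from baseline by" and use at least 30 and at least 60 ms. The absolute limits mention neither baseline nor sex. The output is Table 14.3.5.1.3, titled "Proportion of Subjects with Noteworthy QT and QTcF Values and Changes from Baseline by Visit".

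Three other places bear on this:

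- **Protocol 4.2, criterion 20.** A screening QTcF above 450 ms excludes a man, but a woman is excluded only above 470 ms. Heart rates of 45 or less, or of 100 or more, are also exclusionary, with investigator discretion at the low end. No limit is set on uncorrected QT.
- **Protocol 3.4.1.2.** The on-treatment definition reads "Evidence of QT-interval prolongation, defined as an increase in the" QTcF interval of more than 60 ms from Visit 1. It is both rate-corrected and relative to baseline.
- **SAP 4.3.6.** A laboratory abnormality is treatment-emergent only if baseline was normal or is missing. The ECG limits have no such rule.

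**The concern.** A categorical QT table is read for subjects who moved into a range of interest on treatment. Two features of this one blur that reading.

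First, a value above 450 ms counts whether or not the subject was already above it at entry, and the entry criteria knowingly admit some women who were.

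Second, uncorrected QT lengthens as heart rate falls. If the word joining QT and QTcF is programmed literally, as one row met by either interval, subjects with a slower pulse and an unchanged QTcF appear beside subjects with a real QTcF change. Entry values should balance across randomized arms on average and so mainly add noise. A drug effect on heart rate would not balance, and could show up as a difference between arms in this table.

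Safety is part of the primary objective and the arms are small, so a few such subjects would be visible in the percentages.

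**Working it through.** The plan gives no figure for this table, so there is nothing to reproduce. The check compares the entry limits with the criteria, then inverts the Fridericia correction that the SAP names.

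**1. Unchanged entry QTcF against the absolute limits.** The highest QTcF that can enter is 450 ms for men and 470 ms for women.

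| Limit | Man, unchanged QTcF | Woman, unchanged QTcF |
|---|---|---|
| >450 | cannot count | counts if entry QTcF is 451–470 |
| >480 | cannot count | cannot count |
| >500 | cannot count | cannot count |

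For QTcF the problem is therefore confined to one row and one sex.

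**2. Heart rate alone.** QTcF = QT / (60/HR)^(1/3), so QT = QTcF × (60/HR)^(1/3). The QTcF and heart-rate values below are illustrative assumptions.

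Change criteria, with QTcF constant at 410 ms:

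- At 75 bpm: 410 × (60/75)^(1/3) = 380.6 ms.
- At 55 bpm: 410 × (60/55)^(1/3) = 422.1 ms. The rise is 41.5 ms, which meets the 30 ms row.
- From 75 bpm, QT rises by exactly 30 ms at 60 / (410.6/410)^3 = 59.7 bpm, and by 60 ms at 60 / (440.6/410)^3 = 48.3 bpm.
- Across QTcF 390–450 ms and starting rates of 65–90 bpm, a drop of about 12–20 bpm meets the 30 ms row and about 21–35 bpm meets the 60 ms row.

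Absolute limits:

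- QT exceeds 450 ms when the rate is below 60 / (450/QTcF)^3. That is 48.8 bpm at QTcF 420, 52.4 at 430 and 56.1 at 440.
- At 46 bpm, the lowest whole-number rate not excluded, QTcF 440 gives QT 480.7 ms (above 480) and QTcF 470 gives 513.5 ms (above 500).

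Uncorrected QT can thus meet all five criteria with no change in QTcF.

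**3. Size.** 95 subjects over four arms is 23.75, about 24 per arm, so one subject is 1/24 = 4.2 percentage points. The documents give no distribution of QTcF or heart rate, so the number affected cannot be derived. As a range only: if QTcF in women were normal with mean 410–425 and SD 15–20, truncated at 470, then 0.4% to 9.5% of women would enter at 451–470. If half of each arm were women (also an assumption), that is 12 × 0.004 to 12 × 0.095, or about 0.05 to 1.1 women per arm.

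**The case against.** The other side has a good case on several points.

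- **Baseline.** A reader might infer that the table disregards baseline. It does not: two of its five criteria are increases from baseline, and its title says so. Only the three absolute rows lack a baseline condition.
- **Hidden effect.** A reader might infer that a true QTcF difference could be lost in heart-rate noise. The same section summarizes change in heart rate, QT and QTcF by arm at each evaluation and lists every ECG, so a QTcF shift would be seen directly, with any heart-rate shift beside it. This stands.
- **Pooling.** The SAP never says that QT and QTcF form one row. Its introductory sentence and the table title name both intervals and fit separate rows equally well. If the rows are separate, the QTcF rows are free of the rate problem. The wording is ambiguous rather than wrong, but it still leaves the choice to the programmer.
- **Label.** The table calls these values noteworthy. It does not call them QT prolongation.
- **Protocol criterion.** A reader might see a conflict with the rule in Protocol 3.4.1.2. That rule governs individual subjects, and a group summary need not copy it. For QTcF, at least 60 and more than 60 differ only at exactly 60 ms, so the SAP row captures everyone who meets the protocol rule.
- **Frequency.** ECGs follow at least five minutes of supine rest, and nothing in the documents shows how often large falls in rate occur. The table is descriptive, with no test or decision rule attached.

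What survives is the missing new-crossing condition and the unresolved wording.

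**Conclusion.** The point holds in a limited form. The absolute limits count unchanged entry values, which for QTcF affects only women admitted at 451–470 ms and only the 450 row. All five criteria accept uncorrected QT, so under a pooled reading a fall in heart rate alone can meet them. The pooled reading is possible, not stated.

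The impact is low to moderate. It concerns one descriptive table, each affected subject moves an arm's rate by about 4 points, and the continuous summaries give a reader the means to see what happened. The heart-rate examples rest on assumed QTcF and rate values, and the share of women affected rests on an assumed distribution. The documents do not support replacing the 30 and 60 ms cut-offs or removing uncorrected QT from the table. Whether the list matches the guideline it cites was not assessed, because that source is not part of the documents.

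**What to change.** Amend SAP 6.3.3 and the shell of Table 14.3.5.1.3 before unblinding:

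1. Report QTcF in its own rows as the main display, with uncorrected QT in separately labelled rows.
2. For each absolute limit, add the count of subjects above it post-baseline whose baseline was at or below it. This follows the logic of the SAP's own laboratory rule; state how a missing baseline ECG is handled.
3. Show the 450 ms row by sex, since the entry limit differs by sex.
4. Keep the existing rows for increases of at least 30 and at least 60 ms. If the criterion in Protocol 3.4.1.2 is to be reported, add a row for a QTcF increase of more than 60 ms.

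The cost is SAP wording and one table shell, with no new data. The new-crossing counts will include slightly fewer subjects than the plain counts.
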